	
run-in period (participants will not know the identity of the study drug being administered) to obtain select baseline measurements followed by a 5 to 6 week single-blind dose titration period during which lixivaptan administered twice daily will be titrated to the highest tolerated dose. The minimum dose to enter the Double-blind, Randomized Treatment Period is 100 mg BID. Those participants successfully titrated and tolerating the study drug will then be randomized (2:1) to either continue lixivaptan or switch immediately to matching placebo in a double-blind manner. Randomization will be stratified for Chronic Kidney Disease (CKD) Stage and Mayo Clinic ADPKD Image Classification. Double-blind treatment will continue for 52 weeks after which study drug will be held, and final eGFR assessments will be obtained off-treatment during 3 follow-up visits starting on the 8th day after the last dose of double-blind study drug through the 28th day after the last dose of double-blind study drug.
 
Part 2: All participants (placebo and lixivaptan-treated) entering Part 1 will continue into Part 2 of the study and be treated with the active drug, lixivaptan, for an additional 52 weeks (following the Lixivaptan Re-titration Period) unless study drug was previously discontinued for a safety reason, or a participant withdraws consent. Assuming 90% of participants complete the Double-Blind Treatment Period (Part 1), approximately 1215 participants are projected to continue into Part 2. At the beginning of Part 2, all participants will start lixivaptan during the Lixivaptan Re-titration Period to re-establish the dose level that was tolerated during Part 1. The dose will be increased at weekly intervals until the dose level taken at the end of the Double-blind, Randomized Treatment Period in Part 1 is achieved. In order to maintain blinding of the treatment assignment from Part 1, re-titration during Part 2 will continue to be managed by the Interactive Response Technology (IRT) system.
 
Following re-titration, participants will continue on lixivaptan therapy for 52 weeks in the Maintenance Treatment Period of Part 2 and will be assessed at a study visit every 4 weeks. At the end of 52 weeks, study drug will be held, and final assessments will be obtained over 3 follow-up visits starting on the 8th day following the last dose of study drug through the 28th day after the last dose of study drug.

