- a. Lixivaptan Titration Period will last 5 to 6 weeks. At Visits 4 to 8 the lixivaptan dose will be titrated to achieve the highest tolerated dose. All participants will start at Level 1 (50 mg BID) at the end of V3 and will be titrated weekly through Level 2 (100 mg BID), Level 3 (150 mg BID), and Level 4 (200 mg BID), based on tolerability. The minimum dose to enter the Double-blind, Randomized Treatment Period is Level 2. If tolerability is limited at the 2 highest dose levels (Level 3 [150 mg BID] and Level 4 [200 mg BID]) by aquaretic effects, reduction of the evening dose is allowed: to Level 3a (150/100 mg [AM/PM]) or Level 4a (200/150 mg [AM/PM]), respectively. Further dose reductions are allowable as shown in the [Lixivaptan Titration Period \(Part 1\) — Lixivaptan Titration Flowchart](#). **Note:** In the event of tolerability issues at any time during the study, dosing may be decreased or temporarily stopped. If dosing is resumed during the Double-Blind Treatment Period at a dose level less than that achieved at Visit 9, attempts will be made every 4 to 8 weeks to re-establish the previously achieved dose level from Visit 9, if medically appropriate. If study drug is interrupted for longer than 8 weeks, then study drug treatment will be permanently discontinued.
- b. During the study drug-free Follow-up Period I, 3 visits will occur to obtain the 3 serum creatinine values for calculation of eGFR to determine the primary endpoint. The first visit (V23) will occur on the 8th day (+ 3 days) after the last dose of study drug and the last visit (V25) will occur on the 28th day (\pm 3 days) after the last dose of study drug. V24 must be scheduled to occur at least 24 hours after V23 and at least 24 hours prior to V25. At the final visit (V25), the listed additional safety and efficacy assessments will be completed. Participants who have not discontinued due to an AE or withdrawn consent will then continue into the Re-titration Period of Part 2 by resuming study drug dosing at Level 1 (50 mg BID).
- c. At Visit 1a all indicated information will be collected to determine preliminary eligibility and the baseline MRI to determine TKV and LV will be scheduled.

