Double-blind, Randomized Treatment Period (Visits 10 to 22): Following successful completion of titration, participants will be randomized 2:1 (lixivaptan: placebo) to continue to receive lixivaptan at the dose achieved at the end of the Lixivaptan Titration Period or to matching placebo in a double-blind fashion for 52 weeks. Study visits will be scheduled every 4 weeks during this period. Assessments at each visit are detailed in the [Schedule of Procedures – Part 1](#).

Follow-up Period I (Visits 23 to 25): Three visits will occur over a 28-day, study drug-free period following the last dose of study drug. Blood samples will be drawn at 3 time points for serum creatinine and serum cystatin C, to determine eGFR for primary and exploratory analyses, respectively. The first visit (Visit 23) will occur on the 8th day (+ 3 days) after the last dose of study drug, and the last visit (Visit 25) will occur on the 28th day (\pm 3 days) after the last dose of study drug. Visit 24 must be scheduled to occur at least 24 hours after Visit 23 and at least 24 hours prior to Visit 25. At Visit 25, additional efficacy and safety assessments will be performed; a post-baseline MRI for assessment of TKV and LV is to be obtained between 25 days and 31 days post last dose of study drug and must be completed prior to or on the same day as all other Visit 25 study procedures. Following completion of these assessments, all participants (except those who discontinued due to an AE or who have withdrawn consent) will immediately continue into Part 2 at Visit 25.

Note: In the event of tolerability issues at any time during the study, dosing may be decreased or temporarily stopped. If dosing is resumed during the Double-Blind Treatment Period at a dose level less than that achieved at Visit 9, attempts will be made every 4 to 8 weeks to re-establish the previously achieved dose level from Visit 9, if medically appropriate. If study drug is interrupted for longer than 8 weeks, then study drug treatment will be permanently discontinued.

Part 2:

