Participants with a prolonged study drug interruption of greater than 8 weeks will not be allowed to re-initiate and/or re-establish study drug treatment i.e., study drug treatment will be permanently discontinued. These participants should be encouraged to continue their participation in the study following the procedures described in Section 4.2.7 and Appendix 5 (Section 13.5).

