4.2.4 Treatment Discontinuation

Participants may elect to stop treatment, (i.e., stop taking their study drug) permanently before the end of the study for various reasons. This is separate and distinct from study discontinuation and/or withdrawal (Section 4.2.5) although the reason(s) for study drug discontinuation may be identical and/or similar to reason(s) for study discontinuation. Every effort should be made to keep randomized participants in the study and offer them options for continued treatment and, at a minimum, continued study participation to the degree possible as described in Section 4.2.7 and Appendix 5 (Section 13.5) in order to minimize missing data. Participants who permanently discontinue study drug will have the reason for study drug discontinuation (e.g., adverse event) recorded on the eCRF. They will have an ET visit (Visit 22 if in Part 1 or Visit 42 if in Part 2), which should be scheduled within 7 days of the participant's last dose of study drug, to collect data listed in the [Schedule of Procedures – Part 1](#) and [Schedule of Procedures – Part 2](#). Randomized participants who permanently discontinue treatment will immediately proceed into the 4-week Follow-up Period and will complete the 3 visits in the Follow-up Period between Day 8 and Day 28 following the last dose of study drug. The first two visits, Visits 23 and 24 in Part 1 or Visits 43 and 44 in Part 2 (performed no less than 24 hours apart), will be for the collection of serum creatinine and serum cystatin C to determine eGFR, and the third visit, Visit 25 (Part 1) or Visit 45 (Part 2) (performed on Day 28 ± 3 days, and no less than 24 hours from Visit 24 (Part 1) or Visit 44 (Part 2)) will have additional safety and efficacy measurements (including the post-baseline

MRI) in addition to serum creatinine and serum cystatin C eGFR measurements (unless the participant withdraws consent for further data collection).

Following completion of the ET visit and Follow-up Period procedures in Part 1 or Part 2, participants who have permanently discontinued study treatment should be encouraged to remain in the study, in an effort to minimize missing data, and to continue to complete all protocol visits and assessments up to and including their originally scheduled Visit 45 (end of Follow-up Period II). Changes to or initiation of new medications during this time-period should continue to be recorded on the eCRF.

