- Process urine specimen collected by participant as a fasting AM urine specimen the morning of Visit 25 for determination of urine osmolality.
- Confirm the post-baseline MRI for assessment of TKV and LV has been completed.
- Review and assess AEs and SAEs.
- Collect and review new concomitant medication information.
- Collect and review any acetaminophen use information.
- Collect medical resource utilization data since the last visit (i.e., medication use or changes; unplanned office visits; urgent care or emergency department usage and hospitalizations) based on any AEs/SAEs reported.
- Check vital signs.
- Collect body weight measurement.
- Collect urine for:
 - urinalysis;
 - local urine pregnancy test (**Note:** all positive tests will be confirmed by a serum pregnancy test at the central laboratory).
- Perform a brief physical examination.
- Perform a 12-lead ECG.

- Collect blood samples for the following laboratory testing:
 - chemistry, including serum sodium;
 - liver chemistry;
 - serum creatinine and serum cystatin C for eGFR determinations. **Note:** Every attempt will be made to draw blood samples for eGFR determinations at approximately the same clock time during Visits 1a/1b, 2, and 3 and Visits 23, 24, and 25, and again at Visits 43, 44, and 45, for a given participant;
 - hematology.
- Administer the following health-outcomes scales to participants (**Note:** responses should be reviewed prior to completion of the visit in order to clarify any ambiguous or missing responses):
 - ADPKD-IS
 - ADPKD-PDS
 - ADPKD-UIS
- Contact the IRT to register completion of the visit and to obtain 1 study drug kit number to initiate the Lixivaptan Re-Titration Period (Part 2). Dispense open-label study drug. Instruct the participant to take 4 capsules twice a day daily approximately 10 hours apart.
- Remind the participant to increase fluid intake to prevent dehydration
- Schedule the participant for the next visit (to occur in 1 week \pm 2 days). Provide the participant with an appointment reminder card and any written instructions.

6.6 Lixivaptan Re-titration Period – Part 2

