8.4.2 Sensitivity Analysis of the Primary Efficacy Analysis

In particular, in order to address the impact of missing data on the results from the primary efficacy analysis, a number of sensitivity analyses will be performed. The detailed sensitivity analyses for the primary efficacy analysis will be described in the statistical analysis plan (SAP).

Amongst these sensitivity analyses, the main sensitivity analysis of the primary efficacy analysis will use the mean of eGFR values obtained pretreatment and the mean of eGFR values obtained off treatment after the end of the 52-week treatment period, regardless of adherence to randomized treatment and/or withdrawal for all randomized participants, i.e., Intent-To-Treat participants. Missing values at Week 52 will be imputed using multiple imputations (assuming missing at random). Tipping point analyses will be included using a pattern-mixture model to impute missing data at Week 52 (assuming missing not at random) by systematically varying assumptions about the missing outcomes on the two treatment arms – these tipping point analyses will be bi-dimensional, i.e., allow the assumptions about the missing outcomes in the two arms to vary independently, and will include scenarios where the dropouts on the lixivaptan arm have worst outcome compared to placebo dropouts.

8.5 Secondary Efficacy Analyses.

If the primary efficacy analysis is statistically significant at the 1% level of significance, then the secondary efficacy endpoints of (1) annualized rate of change (slope) in eGFR based on all on-treatment eGFR determinations during the Double-blind, Randomized Treatment Period calculated from the CKD-EPI_{cr}_R equation for serum creatinine; and (2) annualized change in TKV as measured by MRI will be analyzed. Each will be tested at the 1% level of significance in sequential order using a closed testing procedure on the SEAS. The details of the testing procedure will be provided in the SAP for the study.

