4.2. Study Endpoints of the Open-label Phase (Part 2/Year 2)

4.2.1. Key Endpoints

4.2.1.1. Key Comparison Endpoint

The primary endpoint of Part 2 is the annualized change in eGFR calculated from the CKD-EPI equation (2021 CKD-EPIcr_R) for serum creatinine from baseline to the post-treatment follow-up in Part 2, annualized by participant's treatment elapsed duration in Part 2 as defined below. Baseline eGFR in Part 2 is defined as the mean of the 3 eGFR determinations obtained at 3 post-treatment follow-up visits (Visits 23, 24, and 25) after Week 52 in Part 1. The post-treatment follow-up eGFR of Part 2 is defined as the mean of 3 eGFR assessments obtained during the

Follow-up Period II after Week 104 for on-treatment completers or, for participants who discontinue study drug treatment prior to Week 104 [Visit 42], during the Follow-up Period 8 to 28 days following study drug treatment discontinuation in Part 2. The participant's treatment elapsed duration in Part 2 is defined as the number of years (number of days divided by 365.25) from the median of the collection dates of the baseline eGFR assessments to the median of the collection dates of the 3 eGFR assessments obtained during the post-treatment follow-up.

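### The protocol gives conflicting rules on whether a participant who stops double-blind drug early for a non-AE reason receives open-label lixivaptan at an early Visit 25, and the Week-52 off-treatment sensitivity analysis depends on which rule is followed

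*Protocol*

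**What the plan says.** **Rules that lead to Part 2 drug.** Protocol 3.1.2 (Follow-up Period I) states that "all participants (except those who discontinued due to an AE or who have withdrawn consent) will immediately continue into Part 2 at Visit 25". Table 3 footnote b has the same exception and says that dosing then resumes at the lowest level. The synopsis (Study Design, Part 2) treats everyone with lixivaptan "unless study drug was previously discontinued for a safety reason, or a participant withdraws consent". At Visit 25, section 6.5.2 has the site contact the IRT "to obtain 1 study drug kit number to initiate the Lixivaptan Re-Titration Period (Part 2). Dispense open-label study drug", with no check that the double-blind year was completed.

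**Rules that keep stoppers off drug.** Section 4.2.3 says participants interrupted for more than 8 weeks "will not be allowed to re-initiate and/or re-establish study drug treatment i.e., study drug treatment will be permanently discontinued". Section 4.2.4 moves a permanent stopper straight into the follow-up visits, with Visit 25 at Day 28 (± 3 days) after the last dose. It then says "participants who have permanently discontinued study treatment should be encouraged to remain in the study" and complete the remaining visits up to the originally scheduled Visit 45. Appendix 5 step 4 agrees, and neither mentions further drug. SAP 3.6 speaks of re-titration for those who completed Part 1.

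**Analyses that depend on this.** Protocol 8.4.2 bases the main sensitivity analysis on "the mean of eGFR values obtained off treatment after the end of the 52-week treatment period, regardless of adherence to randomized treatment"; SAP 8.2.1.1 carries it out in the mITT set. SAP 4.2.1.1 takes the Part 2 baseline from "3 post-treatment follow-up visits (Visits 23, 24, and 25) after Week 52 in Part 1". Protocol 8.6.1 uses the Follow-up Period I mean with no Week-52 condition.

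**The concern.** A participant who stops double-blind drug because of trial burden, with no AE and no withdrawal of consent, meets both sets of rules at the Day-28 visit. Under one set the site dispenses lixivaptan. Under the other the participant continues off drug to the original Week 52.

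The exception itself also varies: an AE in 3.1.2, a safety reason in the synopsis. Section 4.2.5 lists pregnancy and lack of efficacy separately from AEs, so it is unclear whether either exception covers them.

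At stake is the analysis meant to show that the primary result does not depend on adherence. It needs an off-treatment value after Week 52 from participants who stopped early. If those participants have been given lixivaptan in the meantime, in either arm, the value is missing or no longer reflects the randomized assignment. About 250 sites and the IRT would be working from instructions that cannot both be applied to the same person.

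**Working it through.** **1. The plan's own figures.** Inputs from protocol 8.1: difference 1.40, SD 6.20, allocation 2:1, significance level 0.01, power 90%. Two-sided, with z values 2.576 and 1.282:

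- placebo n = 1.5 × 6.20² × (2.576 + 1.282)² / 1.40² ≈ 437.7, so 438
- lixivaptan 876, total 1314, as stated (a one-sided test would give 1149)
- 0.90 × 1350 = 1215 continuing into Part 2, as stated

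**2. Calendar under the crossover rule.** For a stop at week w, Visit 25 falls at about w + 4. Re-titration (2 to 4 weeks) ends at w + 6 to w + 8, and the 52-week maintenance period at w + 58 to w + 60.

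| Stop (week) | Visit 25 | Open-label dosing until |
|---|---|---|
| 12 | 16 | 70–72 |
| 26 | 30 | 84–86 |
| 47 | 51 | 105–107 |

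Any stop up to about Week 47 therefore puts the participant on lixivaptan at Week 52. For the Week-12 stopper, the next off-treatment follow-up comes after 54 to 56 weeks of lixivaptan (52 plus 2 to 4). SAP 8.2.1.1 accepts off-treatment follow-up visits after Week 52 and does not exclude values obtained after Part 2 dosing, so that late value could be admitted.

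**3. Calendar under 4.2.4.** The same participant has early Visits 23 to 25 for the primary endpoint and stays on the original calendar. The off-treatment value after Week 52 can be collected.

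**4. Part 2 baseline for a participant who crosses over early.** Under protocol 8.6.1 it exists, from the early Follow-up Period I. Under SAP 4.2.1.1 it is empty, because those visits did not follow Week 52.

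**5. Size.** The synopsis assumes 90% complete double-blind treatment, so 1350 − 1215 = 135 do not, about 45 of them on placebo at equal rates. That count includes AE stoppers and consent withdrawals, who do not cross over. The share stopping for any other reason is not given. Assuming 25%, 50% or 75%:

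- 135 × 0.25, 0.50, 0.75 ≈ 34, 68, 101 participants
- a third of these on placebo: about 11, 23, 34

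**6. Power if these Week-52 values are simply absent**, with effect and SD unchanged and losses in the 2:1 ratio. Power = Φ(1.40 / (6.20 × √(1.5/n)) − 2.576), with n the placebo number:

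- none lost (n = 450): 90.9%
- 34 lost: 90.1%
- 101 lost: 88.2%
- 135 lost (n = 405): 87.2%

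**The case against.** The best defence is that 3.1.2 describes the standard path after a full year, and that 4.2.4 is the specific rule for permanent stoppers. Appendix 5 and section 6.9 fit that reading. Section 4.2.1 foresees Part 2 participants who never begin open-label drug, and SAP 3.6 ties re-titration to completing Part 1. The synopsis also equates the 90% who complete with the 1215 who continue, which leaves no early stopper crossing over. This reading is coherent, but no text adopts it. The synopsis exception is worded around why drug was stopped, and a non-safety stop falls outside it.

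Several objections stand and limit the point:

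- A reader might infer that 4.2.4 forbids re-dosing. It only implies it; the explicit bar is in 4.2.3.
- A reader might apply the Day-28 crossover to an interruption of more than 8 weeks. It does not fit. That stop becomes permanent only after Day 28 has passed, and the Day 8 to 28 samples are interruption assessments during which treatment may restart. The explicit bar and the clear early-crossover timeline therefore concern different participants.
- Missing Week-52 values are already imputed. Protocol 8.4.2 adds a tipping-point analysis for them, but SAP 8.2.1.1 lists only missing-at-random imputation for the Week-52 version. Imputation also does not remove a value collected after Part 2 dosing.
- Part 2 is descriptive, and SAP 8.12 allows further analyses for differing exposure patterns. Limiting the SAP 8.7 table to on-treatment completers would be a preference, and it selects on a post-randomization outcome.

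**Conclusion.** The instructions conflict for participants who permanently stop double-blind drug for a reason other than an AE or safety reason and do not withdraw consent. The documents do not settle which rule applies. The consequence is conditional: if the crossover rule is followed, stoppers up to about Week 47 have no uncontaminated off-treatment value after Week 52, and the SAP's Part 2 baseline is empty for them.

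A reader might go further and infer that the Week-52 value and the Part 2 baseline cannot exist for early stoppers. The documents do not support that: the first can be collected under 4.2.4, and the second exists under protocol 8.6.1. Nor is the primary result affected, since protocol 8.4.1 and SAP 4.1.1.1 use the follow-up immediately after discontinuation.

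The 135 non-completers are an upper bound resting on the synopsis's 90% completion; 34 to 101 rests on an assumed share. The power loss is modest, so the reason to act is the conflict and the meaning of the Week-52 comparison. Stoppers in both arms would be dosed, so the direction of any bias is not fixed. SAP section 12 reports early termination with 5 participants randomized and no statistical analyses, so the point concerns the plan and not reported results.

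**What to change.** 1. Reconcile the synopsis, protocol 3.1.2, Table 3 footnote b, 4.2.3, 4.2.4, Appendix 5 step 4 and SAP 3.6. One rule, chosen by the sponsor, should say whether and when a participant who permanently stopped double-blind drug may receive Part 2 drug, with a single wording of the exception. Align the IRT with it at Visit 25.
2. State in SAP 8.2.1.1 that any eGFR after a first Part 2 dose is not an off-treatment Part 1 value and is treated as missing in the Week-52 analysis. Align the Part 2 baseline wording in SAP 4.2.1.1 with protocol 8.6.1.
3. Optionally, add a supplementary display of the SAP 8.7 durability comparison for Part 1 on-treatment completers, keeping the planned P2EAS table.

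The cost is a protocol wording amendment, an IRT check and two SAP edits. Under a rule that lets early stoppers cross over, their Week-52 values would be imputed.
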